### 10.2. Schedule of Assessments

The schedule of study assessments/procedures for this study is presented in [Table 2](#).

Assessments in the study are intended to be conducted in clinic; they may be conducted remotely under extenuating circumstances (eg, COVID-19 restrictions), which will be determined individually for each site and/or subject.

**Table 2: Study BCX9930-205: Schedule of Study Assessments/Procedures**

Assessment/Procedure	Baseline Day 1 a	Treatment Period (Weeks 8, 16, 24, 32, 40, 48, 60, 72, 84, and 96 b )	EOS/ET c
Written informed consent	X		
Review eligibility criteria	X		
Medical & medication history d	X		
HBV, HCV, HIV viral load testing e			
Height, body weight & BMI	X		
Symptom-directed physical examination f	X	X	X
Vital signs g	X	X	X
Clinical chemistry h /hematology i /coagulation/ urinalysis including microscopy j	X	X	X
Pregnancy test k	X	X	X
FSH test l	X	X	X
Study drug administration m			
Study drug accountability	X	X	X
Record AEs, concomitant medications & transfusions	X	X	X

Abbreviations: AE = adverse event; BID = twice daily; BMI = body mass index; EOS = end of study; ET = early termination; FSH = follicle-stimulating hormone; HBV = hepatitis B virus; HBC = hepatitis C virus; HIV = human immunodeficiency virus; ICF = informed consent form; PNH = paroxysmal nocturnal hemoglobinuria; RBC = red blood cell; WBC = white blood cell.

a The last on-treatment visit completed for the prior study will also serve as the baseline visit for Study 205. Therefore, procedures at the last on-treatment visit in the prior study and any specific assessments for Study 205 will be conducted at this visit. If there will be a lapse between the end of the prior study and rollover into Study 205 such that the baseline visit for Study 205 is not conducted coincident with the last on-treatment visit in the prior study, the site must contact the sponsor medical monitor (or designee) to determine whether the subject will be eligible to participate in Study 205. If eligible and subsequently enrolled into Study 205, the subjects must complete the Study 205 baseline visit. The sponsor medical monitor (or designee) will recommend which procedures need to be performed at that visit.

b Visits may be performed within a window of  $\pm$  6 days. Subjects who have not completed 24 weeks of treatment with BCX9930 prior to entering this study must return to the clinic every 4 weeks until they have completed 24 weeks of cumulative treatment. Subjects with **CCI** [REDACTED] will be required to complete additional assessments **CCI** [REDACTED] at the investigational site, or at a remote laboratory more convenient for the subject as indicated in Section 10.3.1 and Section 12.5.2. Additional visits may be required for subjects who experience hemolysis on study or following the permanent discontinuation of BCX9930, or who require unscheduled visits for additional or repeat evaluations. Subjects do not need to withhold any BCX9930 doses on clinic days or take a dose in the clinic, unless the clinic visit falls during the subject's normal time of dosing.

c Subjects who discontinue dosing with BCX9930 for any reason (complete study visits or discontinue early), will be asked to complete an EOS or ET visit, as applicable, approximately 3 weeks ( $\pm$  3 days) after last dose of BCX9930.

d Medical and medication history will be obtained from the prior study.

e For those who entered the prior study with positive serology for HIV or active infection with HBV or HCV, the appropriate testing for viral load should be repeated approximately yearly from the date of first viral load assessment. If positive, contact the medical monitor to discuss the best option for the subject.

f Symptom-directed physical examinations will be performed at all regularly scheduled visits.

g To include blood pressure, pulse rate, and temperature. Prior to obtaining blood pressure and pulse rate, subjects should rest quietly for a brief period.

h Cholesterol and triglycerides will be measured every 6 months (ie, Weeks 24, 48, 72, and 96).

i PNH RBC and WBC clone size included.

j Urine microscopy will be performed at the central laboratory as reflex testing in the event of an abnormal urinalysis.

k For women of childbearing potential, a urine pregnancy test will be assessed at baseline, at onsite visits during the treatment period, and at the EOS/ET visit. Women of childbearing potential will be provided with urine pregnancy test kits for home testing once a month.

l FSH may be assessed at any visit if menopausal status changes to confirm menopausal status. The subject must have a negative urine pregnancy test as per protocol until menopausal status is confirmed.

m BCX9930 will be administered orally at a total dose of 400 mg BID without regard to food.

### 10.3. Study Visits

Unless indicated otherwise, all subjects are expected to complete all scheduled study assessments/procedures.

Written informed consent must be obtained from each subject before initiation of any assessments or procedures conducted specifically for Study 205. Where practical to do so, informed consent should be obtained a minimum of 4 weeks prior to the end of the prior study to allow the sponsor adequate time to provide new study drug and other supplies to the site.

The current study will consist of the following visits:

- Baseline Visit (Day 1)
- On-study Visits
  - Occurring in clinic every 8 weeks at Week 8 (Day  $57 \pm 6$  days), Week 16 (Day  $113 \pm 6$  days), Week 24 (Day  $169 \pm 6$  days), Week 32 (Day  $225 \pm 6$  days), Week 40 (Day  $281 \pm 6$  days), until Week 48 (Day  $337 \pm 6$  days), then every 12 weeks at Week 60 (Day  $421 \pm 6$  days), Week 72 (Day  $505 \pm 6$  days), Week 84 (Day  $589 \pm 6$  days), until Week 96 (Day  $673 \pm 6$  days). Subjects who have not completed 24 weeks of treatment with BCX9930 prior to enrolling in this study must return to the clinic every 4 weeks until they have completed 24 weeks of cumulative treatment.
- Unscheduled Visit
  - Subjects should be instructed to immediately contact the investigator if they have new or worsening symptoms of hemolysis. Following the permanent discontinuation of BCX9930, subjects may be required to complete an additional visit(s) to assess for acute symptomatic hemolysis if and when symptoms occur (see Section 12.5.3).

CCI

CCI

CCI

- EOS/ET Visit
  - Subjects who discontinue dosing with BCX9930 for any reason (complete study visits or discontinue early), will be asked to complete an EOS or ET visit, as applicable, approximately 3 weeks ( $\pm 3$  days) after last dose of BCX9930.

For the assessments to be performed at each visit, see [Table 2](#).

### 10.3.1. Additional Assessments for Renal and Hepatic Safety Monitoring

CCI

CCI

CCI

The minimum procedures to be completed at each assessment will depend on whether the subject is assessed at the investigative site or remotely.

For subjects assessed at the investigational site:

- Review/record AEs, concomitant medication use, and blood transfusions
- Vital signs (resting blood pressure, pulse rate, and temperature)
- Blood collection for clinical laboratory evaluations
  - Clinical chemistry
- Urine collection for clinical laboratory evaluations:
  - Urinalysis including microscopy
  - Urine albumin to creatinine ratio (uACR)

For subjects assessed remotely:

- Blood collection for clinical laboratory evaluations:
  - Clinical chemistry (to include at a minimum: sCr, eGFR, blood urea nitrogen, ALT, AST, ALP, and bilirubin [total and direct])
- Urine collection for clinical laboratory evaluations:
  - Urinalysis (to include at a minimum specific gravity, pH, protein, and blood)
  - uACR

## 11. STUDY ASSESSMENTS

### 11.1. Chronology of Assessments

Clinic procedures, such as physical examinations, and vital signs measurements, should be completed prior to any blood collection.

### 11.2. Demographic Information, Medical and Medication History

Demographic information and medical and medication history will be obtained from the prior study. Medication review and review of inclusion and exclusion criteria and prohibited and restricted medications will also be updated and rechecked at baseline (Day 1). For subjects completing a Study 205-specific baseline visit, demographic information and medical and medication history will be rechecked at baseline (Day 1) and updated.

A PNH history will have been taken in the prior study to document PNH clinical characteristics and disease burden.

#### 11.2.1. Contraception Requirements

The following represents the minimum contraception that should be used by study participants and their partners. Additional contraceptive requirements (eg, requiring the

female partners of male subjects to additionally use highly effective contraception) may be required by local site practice and/or the governing ethics committee. All participants must follow all country, regional, and local contraceptive guidelines. It is anticipated that that not all contraceptive methods may be available in all countries/regions, so the list should be modified accordingly.

For the purposes of this study, females are considered fertile following menarche and until becoming postmenopausal, unless permanently sterile (ie, premenopausal with one of the following: documented hysterectomy, documented bilateral salpingectomy, or documented bilateral oophorectomy). Documentation can come from site personnel's review of the subject's medical records, medical examination, or medical history interview.

Female subjects must continue to meet at least one of the following requirements:

1. Be a woman of nonchildbearing potential, either postmenopausal (defined as without menses for  $\geq$  12 months without an alternative medical cause with a follicle-stimulating hormone [FSH]  $> 40$  mIU/mL) or had a hysterectomy, bilateral salpingectomy, or bilateral oophorectomy
2. Be a woman of childbearing potential (defined as a female following menarche and prior to becoming postmenopausal who has not had a hysterectomy, bilateral salpingectomy, or bilateral oophorectomy) who agrees to use an acceptable highly effective contraceptive method while enrolled in the study and for a duration of 30 days after last dose of study drug.

Acceptable highly effective contraceptive methods are restricted to the following methods with low user dependency:

- surgical sterilization (ie, bilateral tubal occlusion or vasectomy of the sole male partner and the vasectomized partner has received medical assessment of surgical success)
- IUD or IUS
- implantable progestogen-only hormonal contraception associated with inhibition of ovulation

Exception for South Africa only: Progestogen-only hormonal contraception injection, with active monitoring of compliance, is allowed as a contraceptive method.

Female subjects must abstain from egg donation throughout the study and for a duration of 30 days after last dose of study drug.

Male subjects with a female partner of childbearing potential, unless vasectomized, must use condoms (with spermicide, where available) for the purposes of contraception throughout the study and for a duration of 90 days after the last dose of study drug. It is not known if BCX9930 or BCX13559, the major metabolite of BCX9930, are present in human semen. Therefore, subjects with a pregnant female partner must use condoms to avoid potential exposure of the partner and fetus in utero through semen.

Male subjects must abstain from sperm donation throughout the study and for a duration of 90 days after last dose of study drug.

Abstinence as a contraceptive method will not be an option for subjects regardless of lifestyle or sexual activity.

Per European Clinical Trials Facilitation and Coordination Group guidance, contraception and pregnancy testing requirements must remain in place through the end of relevant systemic exposure ([CTFG 2020](#)). Based on data generated in healthy subjects in Study 101, the geometric mean half-life of BCX9930 was  $\leq 17.35$  hours (suggesting that 5 half-lives are elapsed within approximately 3.6 days). Further, the human mass balance study (Study 102) identified BCX13559 (an acyl glucuronide) as the only major metabolite of BCX9930. Clearance of BCX13559 was determined to be formation-rate limited. Study 102 also showed all subjects achieved  $> 90\%$  recovery of the administered radioactive dose within 12 days (single dose). Together, these findings suggest that the end of relevant systemic exposure for BCX9930 and BCX13559 occurs well before the ET or EOS visit performed approximately 3 weeks after the last dose of BCX9930.

Methods of contraception, as applicable, for both male and female participants should be documented in the source documentation. Investigators will also review each subject's continued use of contraception at periodic intervals to ensure compliance with the protocol contraception requirements, including reminding subjects about the need to renew their contraception.

### **11.3. Virology Assessments**

Antibodies to varicella-zoster virus were tested at the screening visit in the prior study. For this study, any subject who has an exposure to someone with primary varicella (chickenpox) or herpes-zoster (shingles), or who has recently received a live varicella vaccine, should contact the investigator, and administration of varicella zoster immune globulin or other medications should be considered where available.

For those who entered the prior study with positive serology for HIV or active infection with HBV or HCV, the appropriate testing for viral load should be repeated approximately yearly from the date of first viral load assessment. If positive, contact the medical monitor to discuss the best option for the subject.

### **11.4. Effectiveness Assessments**

As currently amended, the protocol no longer requires specific effectiveness assessments to be performed. The clinical benefit of treatment with BCX9930 will be assessed for each individual subject based on the medical judgement of the investigator and the standard-of-care practices for the treatment and management of PNH disease at his or her institution. Common laboratory measurements of PNH will continue to be assessed and reported in the safety testing (eg, Hb, LDH, absolute reticulocyte count, AST, bilirubin, etc.) performed by the designated clinical safety laboratory. Any other laboratory testing should be performed and monitored per appropriate medical judgement. This information will be used to assess the ongoing benefit-risk of continued treatment with BCX9930.

### **11.5. Safety Assessments**

All assessments will be performed as indicated in the schedule of assessments ([Table 2](#)).

#### **11.5.1. Vital Signs**

Measurements of vital signs will include blood pressure, pulse rate, and temperature and should be obtained after the subject has rested for at least 5 minutes in a quiet room at a comfortable temperature, with the subject's arm unconstrained by clothing or other material. Blood pressure measurements will be obtained with the appropriate cuff size, with the

subject's arm supported at the level of the heart, while the subject is resting in a semi-supine position.

#### **11.5.2. Body Weight, Height, and Body Mass Index**

Body weight, height, and body mass index (BMI) will be recorded at the last on-treatment visit in the prior study/baseline. For determination of height and body weight, subjects should be clothed with shoes removed.

#### **11.5.3. Physical Examination**

A targeted (ie, symptom driven) physical examination will be performed at all regularly scheduled assessments to assess for any changes from the previous examination, including, at a minimum, evaluation of new or worsening signs or symptoms.

#### **11.5.4. Clinical Chemistry, Hematology, Urinalysis, and Other Laboratory Assessments**

The following text assumes the use of a central laboratory to support the clinical laboratory testing for safety monitoring, including testing for laboratory measurements of the effectiveness of PNH treatment. However, at investigational sites where it is no longer considered necessary and/or practical to use a central laboratory for the safety oversight of clinical study subjects, local laboratory services may be used. Data will continue to be reported and available to the sponsor to meet ongoing safety review commitments.

Blood and urine samples will be collected during the study. Individual laboratory tests are specified in [Table 3](#). In general, all laboratory samples collected at visits to the investigational site should be collected using kits provided by the designated central laboratory. However, at the investigator's discretion, local laboratories may be used in place of the central laboratory (eg, for logistical reasons such as delays in transport due to COVID-19) or for analysis of samples collected for assessment of possible AEs (eg, when emergent safety concerns require expedited turnaround times for safety laboratory assessments). The additional renal and hepatic safety assessments may be performed at the investigational site or remotely at a location more convenient for the subject. The results from laboratory testing performed at a local or remote laboratory must be provided to the investigational site. The use of a local or remote laboratory in this manner, and any differences in analyte panels with the central laboratory, based on the availability of testing at the local or remote laboratory, will not be considered protocol deviations for the purposes of this protocol. Reference ranges for each local or remote laboratory used will be provided to the sponsor and included in data listings.

Results from the laboratory values should be reviewed as received by the investigator. Evidence of this review should be provided in the source records and may include printing of the laboratory reports with a signature attesting to a review. For out-of-range laboratory findings, the interpretation of clinically significant or not clinically significant should be denoted in the source records. Clinically significant laboratory findings, as assessed by the investigator, should be recorded as AEs as described in the protocol ([Section 12.1](#)).

**Table 3: Clinical Laboratory Evaluations**

Serum Chemistry	Urinalysis with Microscopy a
Albumin	Albumin
Alanine aminotransferase (ALT) (SGPT)	Bilirubin
Alkaline phosphatase (ALP)	Blood
Amylase b	Creatinine
Aspartate aminotransferase (AST) (SGOT)	Glucose
Bilirubin (total and direct)	Ketones
Blood urea nitrogen (BUN)	Leukocytes
Calcium	Nitrites
Chloride	pH
Cholesterol (total, high- and low-density lipoprotein)	Protein
Creatine (phospho)kinase (C[P]K)	Specific gravity
Creatinine (sCr)	Urine albumin to creatinine ratio (uACR)
Glucose	Urobilinogen
Haptoglobin	Pregnancy/Menopause
Lactate dehydrogenase (LDH)	Follicle-stimulating hormone (FSH)
Magnesium	Urine pregnancy test c
Potassium	Coagulation/Fibrinolysis
Sodium	Activated partial thromboplastin time (aPTT)
Protein (total)	Prothrombin time (PT)
Triglycerides	International normalized ratio (INR)
Uric acid	Thrombin time
Hematology	Other Testing
Hemoglobin (Hb)	Estimated glomerular filtration rate(eGFR) d
Hematocrit (Hct)	PNH RBC clone size (total)
Mean corpuscular hemoglobin (MCH)	PNH WBC clone size
Mean corpuscular hemoglobin concentration (MCHC)	Varicella-zoster virus (VZV) immunoglobulin G (IgG) titer (where appropriate)
Mean corpuscular volume (MCV)	Hepatitis B virus (HBV), hepatitis C virus (HCV), human immunodeficiency virus (HIV) viral load (where appropriate)
Platelet count (PLT)	
Red blood cell (erythrocyte) count (RBC)	
Reticulocyte count	
White blood cell count (WBC) with differential	

Abbreviations: DNA = deoxyribonucleic acid; PNH = paroxysmal nocturnal hemoglobinuria; RNA = ribonucleic acid; SGOT = serum glutamic-oxaloacetic transaminase; SGPT = serum glutamic-pyruvic transaminase.

Note: Some analytes may not be analyzed, depending on the availability of validated assays at the designated regional central laboratory

a Reflex to microscopy if dipstick is abnormal. For local laboratory testing, urinalysis analytes may be different.

b If amylase is elevated, reflex to lipase.

c For women of childbearing potential (or as required by local or institutional practice).

d To be calculated by the designated central reference laboratory using the Chronic Kidney Disease Epidemiology Collaboration (CKD-EPI) equation using the serum creatinine method ([Levey and Stevens 2010](#)).

#### 11.5.4.1. Urine Collections for Urinalysis and Urine Microscopy

Investigators should emphasize to staff and the subjects the importance of collecting fresh, high-quality urine specimens (clean-catch, mid-void, etc.) and ensuring appropriate handling and prompt processing of the samples for urinalysis. Urine microscopy will be performed at the central laboratory as a reflex test if the urinalysis testing is abnormal. For subjects with CCI [REDACTED] sites are encouraged to perform urine microscopy using their local laboratory, where appropriate on-site testing capabilities are available, to assess for crystals and/or casts (see also Section 12.5.2).

#### 11.5.5. Menopause and Pregnancy Testing

FSH may be assessed at any visit if menopausal status changes to confirm menopausal status. The subject must have a negative urine pregnancy test as per protocol until menopausal status is confirmed.

For women of childbearing potential, a urine pregnancy test will be assessed at baseline, at monthly intervals during the treatment period, and at the EOS/ET visit, or as required per normal site practice. A serum pregnancy test should immediately be drawn and sent for analysis for any positive urine pregnancy test. Where required, pregnancy testing may be performed using the local laboratory, and using serum testing in lieu of the urine pregnancy tests.

Women of childbearing potential will be provided with urine pregnancy test kits for home testing once a month.

## 12. ADVERSE EVENTS

### 12.1. Definition of Adverse Events

#### 12.1.1. Adverse Event

An AE is any untoward medical occurrence in a clinical study subject. No causal relationship with the study drug/IMP or with the clinical study itself is implied. An AE may be an unfavorable and unintended sign, symptom, syndrome, or illness that develops or worsens during the clinical study. Clinically relevant abnormal results of diagnostic procedures including abnormal laboratory findings (eg, requiring unscheduled diagnostic procedures or treatment measures, or resulting in withdrawal from the study) are considered to be AEs. Abnormal results of diagnostic procedures that are incidental or not clinically relevant are not reportable as AEs. If the diagnostic procedure prompts no additional treatment, visits, or monitoring, it will not meet the definition of an AE.

This includes the following:

- AEs not previously observed in the subject that emerge during the protocol-specified AE reporting period (see Section 12.4.1).
- Findings from protocol-mandated interventions. This can include laboratory assessments performed in the course of the clinical study. AEs should be reported only if the abnormalities are changes from baseline and are clinically significant as described above.
- Pre-existing medical conditions (other than the condition being studied) judged by the investigator to have worsened in severity or frequency or changed in character during

the protocol-specified AE reporting period. When recording such events on an AE/SAE eCRF page, it is important to convey the concept that the pre-existing condition has changed by including applicable descriptors (eg, “more frequent headaches”).

An adverse reaction is defined in International Council for Harmonisation (ICH) E6 guideline as follows: all untoward and unintended responses to a study drug/IMP related to any dose administered. The definition covers also medication errors and uses outside what is foreseen in the protocol, including misuse and abuse of the product. The definition implies a reasonable possibility of a causal relationship between the event and the study drug/IMP. This means that there are facts (evidence) or arguments to suggest a causal relationship.

Hospitalization scenarios do not require reporting as an SAE where there is no occurrence of an AE. These scenarios include a planned hospitalization or prolonged hospitalization to:

- Perform a routine control screening for a pre-existing illness or to diagnose a suspected illness. In the case of the latter, the symptomatology should be reported as an AE and amended if a diagnosis is confirmed.
- Undergo a diagnostic or elective surgical procedure for a pre-existing medical condition that has not changed (eg, a joint replacement for which the subject was on a waiting list).
- Undergo medical observation without the occurrence of an AE due to standard of care in the region or hospital.

Surgical procedures should not be reported as AEs. The condition for which the surgery is required should be reported as the AE if it occurs or is detected during the study period. Planned surgical measures permitted by the clinical study protocol and the conditions(s) leading to these measures are not AEs if the condition(s) was (were) known before the start of study treatment. In the latter case, the condition should be reported as medical history.

AEs are designated as “nonserious” or “serious”.

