### **12.1.2. Serious Adverse Event**

A serious adverse event (SAE) is an AE/reaction that results in any of the following outcomes:

- Death
- Is life-threatening (subject is at immediate risk of death at the time of the event; it does not refer to an event that hypothetically might have caused death if it were more severe)
- Requires subject hospitalization (formal admission to a hospital for medical reasons) or prolongation of existing hospitalization
- Results in persistent or significant disability/incapacity (ie, there is a substantial disruption of a person’s ability to carry out normal life functions)
- Is a congenital anomaly/birth defect

Important medical events that may not result in death, are not life-threatening, or do not require hospitalization may be considered SAEs when, based upon appropriate medical judgment, they may jeopardize the subject’s health or may require medical or surgical intervention to prevent one of the outcomes listed in this definition. Examples of such events

may include allergic bronchospasm requiring intensive treatment in an emergency room or at home, blood dyscrasias, or convulsions that do not result in subject hospitalization.

In addition, the sponsor considers any abortions (elective or spontaneous), fetal demise, and still birth to be SAEs for reporting purposes (see Section 12.4.2).

Some hospitalization scenarios, as outlined in Section 12.1.1, do not require reporting as SAEs.

Overdose will be considered an SAE only if any of the seriousness criteria are met. Any clinical complication in association with the overdose should be reported as an AE or SAE (as applicable) along with the overdose (see Section 12.6). Details of signs or symptoms, clinical management, and outcome should be reported, if available. Overdose without associated signs or symptoms should not be recorded as AEs but should be recorded as protocol deviations.

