### **12.5.3. Risk of Hemolysis After Missed Doses, Treatment Interruption, or Permanent Discontinuation**

Investigators should remind subjects of the potential risk of hemolysis following missed doses (particularly multiple consecutive missed doses) and treatment interruption, and the definite risk after permanent discontinuation of BCX9930. By inhibiting the AP of complement, BCX9930 may improve Hb levels and increase circulating RBC clone size by reducing the hemolysis of PNH RBCs. Missed doses and treatment interruption of BCX9930 may lead to hemolysis. Subjects are at risk of severe hemolysis when BCX9930 is permanently discontinued. Based on available data regarding the PK and PD of BCX9930, severe hemolysis, if it occurs, would be expected to present within days after discontinuation of therapy.

Monitoring for hemolysis should be performed based on the medical judgement of the investigator. However, when subjects permanently discontinue BCX9930 at any time during the study, the following recommendations are made:

- If the subject is asymptomatic, it is recommended that contact with the subject be maintained on a daily basis for a minimum of 7 days. Contact may be conducted by telephone, email, or other means, including in person, if preferred. When any sign or symptom of hemolysis occurs, the subject should be promptly evaluated. Additional monitoring following the first contact after permanent discontinuation should be guided by the medical judgement of the investigator.

- For subjects who are already symptomatic when treatment is discontinued, whether the subject should be assessed in person or can be followed with daily contact will be based on the investigator's medical judgement taking into account the severity of the reported signs or symptoms and/or any reported worsening of the signs or symptoms. When possible, subjects should return to the investigative center; however, when this is not possible, arrangements may be made for the subject to be assessed by his or her local hematologist and a local laboratory used for clinical laboratory testing. When hemolysis occurs after the permanent discontinuation of BCX9930, treatment should be provided according to the judgement of the investigator.

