- Subjects should be asked to contact the investigator if they experience any new or worsening signs or symptoms of hemolysis. Subjects should be evaluated per the investigator's medical judgement. A review of dosing compliance to ensure that the subject is taking the drug should be performed, regardless of the method used to evaluate the subject (ie, in-person or remote assessment). It should also be determined whether the subject has had any recent complement-activating conditions (eg, infection, trauma, or surgery) that may have contributed to the hemolytic event.
- Treatment with BCX9930 should not be interrupted or withheld unless there is an absolute contraindication for continued dosing. Suggestions for anti-emetic therapy for subject with active nausea and vomiting when tablet contents are vomited are given in Section [9.6.2](#).

The sponsor medical monitor should be notified in the event of hemolysis symptoms, any planned treatment interruption, or permanent discontinuation of BCX9930. Any missed doses, treatment interruption, or permanent discontinuation must be recorded in the eCRF and source documents, including the reason for the interruption, missed doses, or discontinuation.

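### Protocol 12.1.1 gives conflicting signals on whether worsening PNH is an adverse event, so hemolysis may be under-counted in the TEAE tables

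*Protocol*

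**What the plan says.** Protocol 12.1.1 opens broadly: "An AE is any untoward medical occurrence in a clinical study subject". It adds: "An AE may be an unfavorable and unintended sign, symptom, syndrome, or illness that develops or worsens during the clinical study". Clinically relevant abnormal results also count ("eg, requiring unscheduled diagnostic procedures or treatment measures, or resulting in withdrawal from the study) are considered to be AEs").

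A list of what the definition includes follows. Its third bullet, the only one on worsening of existing illness, covers "Pre-existing medical conditions (other than the condition being studied) judged by the investigator to have worsened in severity or frequency".

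Protocol 12.1.2 builds on this: "A serious adverse event (SAE) is an AE/reaction that results in any of the following outcomes".

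Protocol 12.5.3 warns: "Subjects are at risk of severe hemolysis when BCX9930 is permanently discontinued". On reporting it says: "The sponsor medical monitor should be notified in the event of hemolysis symptoms, any planned treatment interruption, or permanent discontinuation of BCX9930". It also requires missed doses, interruptions and discontinuations to be entered in the eCRF with their reasons. The visible text does not name an AE or SAE form for the hemolytic event itself.

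On efficacy, Protocol 11.4 states: "As currently amended, the protocol no longer requires specific effectiveness assessments to be performed". It goes on to say that common PNH laboratory measures remain in the safety panel.

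**The concern.** Every subject has PNH, and Protocol 5.1 describes hemolysis as a consequence of the disease. A hemolytic episode can therefore be read in two ways: as an untoward event under the opening definition, or as worsening of the studied disease, which the third bullet leaves out.

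Setting disease worsening apart from AEs does little harm when an efficacy endpoint captures it. Here the specific effectiveness assessments have gone and no hemolysis event is defined. The endpoint is the incidence of TEAEs, laboratory abnormalities and other safety findings.

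Stopping is not rare in this study. Treatment under the current protocol ends at 96 weeks at the latest, and 12.5.3 treats the hemolysis risk after permanent discontinuation as definite rather than potential. If sites read the bullet differently, the hemolysis count in the TEAE tables would partly reflect local recording habit.

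**Working it through.** **1. Does the text settle the matter?** The relevant provisions, side by side:

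- *For recording:* the opening definition has no PNH exception. Abnormal results that prompt unscheduled work-up or treatment are AEs. The second bullet covers clinically significant changes from baseline in protocol-mandated tests, and 11.5.4 says that clinically significant laboratory findings should be recorded as AEs. Hemoglobin, LDH, haptoglobin, bilirubin and reticulocytes are all in Protocol Table 3.
- *Against recording:* the parenthesis in the third bullet. It has no evident purpose unless worsening PNH is to be handled differently.
- *Silent:* 12.5.3 asks for evaluation, monitor notification and eCRF entry of dosing events, but says nothing about AE entry for hemolysis. Elsewhere the protocol does give explicit recording rules, for example for overdose and pregnancy outcomes.
- *Unknown:* the events of special monitoring in 12.1.3 are redacted.

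The visible text therefore supports recording more strongly than not, but it does not resolve the conflict.

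**2. Does it reach SAEs?** An SAE must first be an AE or reaction. Section 12.1.1 also says that certain hospital stays need no SAE report when no AE has occurred, including observation under local standard of care. A site that has already decided hemolysis is not an AE could apply that rule to an admission. This step depends entirely on the exclusionary reading.

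**3. Would other outputs catch it?**

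- Protocol 12.5.3 expects severe hemolysis within days of stopping. The end-of-study or early-termination visit is about 3 weeks after the last dose (Protocol 10.3).
- The SAP tables of hemoglobin and LDH (7.1, 7.2.1) cover scheduled treatment-period visits. Unscheduled values are only listed, and hemoglobin within 14 days after transfusion is left out of the summary.
- Laboratory abnormalities appear only as a Grade 3 or 4 listing (SAP 9.1.2), with no incidence table in SAP 9.1.1. Transfusions are listed.
- SAP 5.6.4 counts AEs during taper and up to 30 days after the last dose. That window would capture withdrawal hemolysis, but only if it was entered as an AE.

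**4. Size.** The plan states no hemolysis rate, so there is no figure to reproduce. The maximum enrollment is 30 (Protocol 13.1). One unrecorded subject changes the incidence by 1/30 = 3.3 percentage points.

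For scale only, let p be the share of subjects with hemolysis and r the share of those recorded as AEs. Both are assumptions. Expected recorded subjects = 30 × p × r. The chance of at least one recorded subject = 1 − (1 − p × r)^30.

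| p | all recorded (r = 1) | half recorded (r = 0.5) | none recorded (r = 0) |
|---|---|---|---|
| 5% | 1.5; 0.785 | 0.75; 0.532 | 0; 0 |
| 10% | 3; 0.958 | 1.5; 0.785 | 0; 0 |
| 20% | 6; 0.999 | 3; 0.958 | 0; 0 |
| 40% | 12; >0.999 | 6; 0.999 | 0; 0 |

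Each cell gives expected subjects, then the chance of at least one. A table showing 0/30 would suggest an upper 95% limit of 1 − 0.05^(1/30) = 9.5% (one-sided) or 1 − 0.025^(1/30) = 11.6% (two-sided exact), whatever the true rate, if the zero came from non-recording.

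**The case against.** The strongest reply is that the parenthesis limits one bullet in an inclusive list and is not an exclusion. Where this protocol wants something kept out of AE recording it says so directly, as it does for incidental results, surgical procedures and overdose without symptoms. It has no such sentence for PNH or hemolysis. An episode that leads to transfusion or unscheduled work-up fits the laboratory-finding rule, and 12.1.2 names blood dyscrasias among its examples of important medical events.

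This stands, and it rules out several stronger readings that a reader might infer:

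- *That the protocol exempts hemolysis from AE recording, or that an admission for hemolysis falls outside SAE reporting.* Both follow only if a site turns the parenthesis into an exclusion, against the opening definition.
- *That hemolysis would vanish from the only endpoint.* Protocol 6.2 also includes laboratory abnormalities, vital signs and physical findings. Hemoglobin and LDH are tabulated, and transfusions are listed.
- *That the reported rate is biased low.* It may be understated. Nothing in the documents shows how sites actually recorded these events.
- *That hemolysis is the main risk.* Protocol 5.3 also calls meningococcal infection a significant risk, and renal and hepatic events have their own sections.
- *That the protocol contains no rule at all.* The redacted special-monitoring list prevents that claim.

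What the reply does not supply is a visible sentence telling a site to enter hemolysis as an AE.

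**Conclusion.** The concern holds as an internal conflict in Protocol 12.1.1 that should be reconciled. The general definition and the laboratory-finding rule cover hemolysis, the bullet on worsening illness leaves out the studied disease, and no visible text decides between them. The TEAE count of hemolysis may be understated, by 3.3 percentage points for each unrecorded subject if 30 are enrolled, and SAE reporting may be affected in the same way. The total shortfall is unknown because the documents give neither a hemolysis rate nor a recording rate. The laboratory and transfusion outputs soften the problem but are weakest in the days after stopping. The conclusion assumes that at least some sites read the parenthesis as an exclusion and that no overriding rule sits in the redacted text.

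**What to change.** - **Wording.** In Protocol 12.1.1, delete the parenthesis in the third bullet. Alternatively, add a sentence such as: Hemolysis and other worsening of PNH are recorded as AEs, and as SAEs when a seriousness criterion is met.
- **Reconciliation before database lock.** Check medical-monitor hemolysis notifications, transfusion records and discontinuation records against AE entries, and query any mismatch with the site.
- **Reporting.** State in the abbreviated study report how hemolysis was counted. If an amendment is no longer practical, the reconciliation and this statement still repair most of the problem.

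The cost is one sentence in an amendment or site memo and a small query effort in at most 30 subjects. The AE count may rise slightly.
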